13.5 Analysis of Physical and Neurologic Examination Results

Physical examination will be summarized by body system by safety evaluable subgroups and overall. The number and percentage of subjects will be presented. The physical exam findings will also be presented in a by-subject listing including the verbatim text for each physical exam event.

Observations from the full physical, and brief/full neurological examinations will be listed on a by-subject basis. The full examination findings will also be summarized at baseline and follow-up for each body system for physical examination and neurologic parameter (level of consciousness, mental status, visual fields etc.) for the full neurologic examination by safety evaluable subgroups and overall for the safety population.

Neurological examination results will be tabulated as number and percentage of subjects with normal, abnormal non-clinically significant, abnormal clinically significant for each one of the exams for each post-baseline visit.

Physical examination results will be tabulated as number and percentage of subjects with normal, abnormal non-clinically significant, abnormal clinically significant for each one of the exams for each post-baseline timepoint. Post-baseline timepoints will be derived as per rules included in [Section 10.3](#).

In addition, a shift table of physical examination from baseline to post-baseline timepoint will be prepared using the normal, abnormal non-clinically significant, abnormal clinically significant categories for each one of the exams.

A shift table displaying the changes from baseline to follow-up in physical examination findings will also be presented by body system by safety evaluable

subgroups and overall. A similar table will be prepared for the brief neurologic exam findings.

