statistically significant reduction in the frequency of partial onset seizures (Table 2) and seizure free rates (Table 3). YKP3089 was generally well-tolerated. The rate of adverse event withdrawals was similar between the YKP3089 and placebo groups. No life threatening serious adverse events were identified among YKP3089-treated subjects. The most common central nervous system adverse events in the YKP3089 group were somnolence, dizziness, fatigue, and gait disorder.

The second randomized, double-blind, placebo-controlled, dose response trial with a 18 week treatment period enrolled a total of 437 subjects, 108 in a 100 mg YKP3089 group, 110 in a 200 mg YKP3089 group, 111 in a 400 mg YKP3089 group and 109 in a placebo group. The trial confirmed that treatment with 200 mg/day and 400mg/day of YKP3089 produces a highly statistically significant reduction in the frequency of partial onset seizures in patients with partial epilepsy (Table 2) and high seizure free rates (Table 4).

Table 2: Effect Size of Median Percent Reduction and 50% Responder Rate Relative to Placebo in YKP3089 Trials

	YKP3089C013 Study	YKP3089C017 Study		
Dose	200mg	100mg	200mg	400mg
Median Percent Reduction	34.1	11.5	31.0	31.0
50% Responder Rate	28.2	19.0	35.2	38.7

P values in all comparisons were <0.01

Table 3: Seizure free Rates (Completer Population) at 200mg in YKP3089C013

Responder Type	6 Week Maintenance Phase		
	% Responders placebo N = 99	% Responders YKP3089 N = 102	P value
100%	9.1	27.5	0.0003

Table 4: Seizure Free Rates (Completer Population) in YKP3089C017

Responder Type	12 Week Maintenance Phase			
	% Responders	% Responders (YKP3089 100 mg)	% Responders	% Responders

There have been three cases of DRESS syndrome in YKP3089 clinical studies.

Rash and hypersensitivity During the YKP3089 development program there have been other reports of rash and hypersensitivity reactions, some resulting in hospitalization and/or discontinuation. An aggregate analysis of the rate of rash/hypersensitivity and DRESS in subjects exposed to multiple doses of YKP3089 was performed Table 5.

Table 5: Rate of rash/hypersensitivity and DRESS in subjects exposed to multiple doses of YKP3089

	Starting Dose 50 mg with 50 mg Increase Every 2 Weeks		Starting dose 50 mg with 50 mg Increase Every 1 Week		Starting dose 100 mg or more with 100 mg Increase Every 5 to 7 Days		Total	
	Active	Placebo	Active	Placebo	Active	Placebo	Active	Placebo
Subjects Exposed	120	112	363	152	350	37	833	301

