9.1 Screening

9.1.1 *Visit 1, Day -21*

As shown in [Table 1](#), the following will be performed during Visit 1:

- Obtain informed consent (obtained from the subject prior to any study-related procedures)
- Review and record inclusion and exclusion criteria
- Record medical and seizure history and demographics
- Record vital signs
- Conduct full physical examination (see [Appendix A](#)), including height and weight
- Conduct full neurologic examination (see [Appendix B](#))
- Administer C-SSRS (Baseline/Screening version) (see [Appendix D: COLUMBIA SUICIDE SEVERITY RATING SCALE \(Baseline/Screening\)](#))
- Perform 12-lead ECG once
- Perform serum pregnancy test (female subjects of childbearing potential; if positive, subject will not be enrolled)
- Draw blood for laboratory safety assessment
- Obtain urine for urinalysis

- An MRI or CT scan will be performed during screening if the subject has not had a neuroimaging study within 10 years of Visit 1. This will be used to document the absence of an active brain lesion, and a copy of the report will be made available to the Sponsor
- Include the EEG report in the source document. If an EEG report cannot be obtained, and the subject is otherwise eligible, an EEG may be performed during screening.
- Record concomitant medications
- Schedule Visit 2 to occur within 3 weeks of Visit 1

9.1.2 *Visit 2, Day 1*

All subjects who have not discontinued will be scheduled to appear at the clinic for Visit 2. At Visit 2, subjects who continue to meet all of the inclusion criteria and none of the exclusion criteria will receive study drug.

As shown in [Table 1](#), the following will be performed at Visit 2:

- Review and record inclusion and exclusion criteria
- Record vital signs
- Conduct brief neurologic examination if required (Appendix C)
- Administer C-SSRS (Since Last Visit version) (Appendix E)
- Perform urine pregnancy test (for female subjects of childbearing potential)
- Record concomitant medications
- Record AEs
- For subjects taking phenytoin or phenobarbital, draw blood for phenytoin or phenobarbital trough levels
- For subjects taking concomitant AEDs other than phenytoin or phenobarbital at US sites only, draw blood for concomitant AEDs (oxcarbazepine, topiramate, lamotrigine, lacosamide, clobazam, perampanel and levetiracetam only) levels
- Dispense study drug as instructed by IWRS if all of the inclusion criteria and none of the exclusion criteria are met

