Visit 15 represents the Follow-up Visit after discontinuation of study drug. This final visit will take place 14 days after the subject's last dose of YKP3089—at any time during the open-label treatment or after 12 months of open-label treatment if there is no additional treatment beyond that point.

As shown in [Table 1](#), the following assessments will be performed at Visit 15:

- Record vital signs
- Measure weight
- Conduct full neurologic examination
- Administer C-SSRS (Since Last Visit version)
- Serum pregnancy test (for female subjects of child-bearing potential)
- Draw blood for laboratory safety assessment
- Record concomitant medications
- Perform drug accountability if tapered
- Record AEs

No study drug will be dispensed.

9.1.16 *Open-Label Extension Beyond Year One*

Subjects who complete Visit 14 and will continue in the open-label treatment beyond year one will adhere to the following visit schedule. The investigator will schedule a return visit in 3 months. Subjects will have study visits every 3 months for a total of 4 visits per study year. The investigator will perform some or all of the following assessments depending up on the visits.

Perform the following every 3 months from Visit 14

- Record vital signs
- Conduct brief neurologic examination if required
- Administer C-SSRS (Since Last Visit version)
- Perform urine pregnancy test (for female subjects of childbearing potential)

- Record concomitant medications
- Perform drug accountability
- Record AEs
- Dispense open-label study drug bottles as instructed by IWRS

Perform the following every 6 months from Visit 14

- Measure weight
- Draw blood for laboratory safety assessment

Perform the following every 12 months from Visit 14

- Perform full physical exam
- Perform 12-lead ECG once
- Obtain urine for urinalysis

This pattern will continue at the discretion of the investigator until development is stopped by SK Life Science Inc, the product is approved for marketing, or anytime at the discretion of SK Life Science Inc.

After the first year of open-label treatment, the visits will be numbered sequentially beginning with Visit 16.

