8.1 Screening and Baseline

At the time of enrollment in the study, all subjects will sign the informed consent.

Demographic data (Date of Birth, Sex, Race and Ethnicity), characterizing enrolled subjects will be collected on the Demographics eCRF.

Height and weight at baseline will be recorded on the Vital Signs eCRF.

The subject's date of past and present medical conditions, prior to study enrollment, will be recorded on a Medical History eCRF. Medical history data will include the Body System, verbatim text, start date, and end date or ongoing.

The subject's epilepsy/seizure history including past and current seizures will be recorded on an Epilepsy/Seizure History eCRFs. Seizure identification and Etiology data will also be collected.

Physical Examination at screening (full examination) will be recorded on the Physical Exam eCRF. These data will include Body System, a normal/abnormal indication, and a description of the abnormality.

All non-AED medications taken by the subject up to the first dose of the study drug will be recorded on the Prior and Concomitant Medications eCRF. These data will include the verbatim medication name, indication for use, dose, route, frequency, start date, and end date or ongoing indication.

A full neurologic evaluation examination will also be performed at screening and recorded on the eCRF. If the subject has not had a recent (within the last 10 years) CT or MRI, one will be performed and entered on the eCRF. An electrocardiogram (EEG) may also be performed and entered on the eCRF. At baseline visit, a brief neurologic examination may be performed (if needed).

Twelve-lead ECGs overall interpretation and results will be collected at screening and will be entered on an eCRF.

Clinical laboratory evaluations (including blood and urine) will be collected at screening and results will be returned electronically for inclusion in the clinical database.

Serum or urine pregnancy test results, where applicable, will be entered into the eCRF.

The baseline version of the Columbia Suicide Rating Scale (C-SSRS) will be assessed at Visit 1 and entered on the eCRF.

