- a. After 12 months of participation in the open-label extension phase, subjects will be re-evaluated. Those who are benefiting from treatment with YKP3089 may continue use of the drug at the discretion of the investigator, until development is stopped by SK Life Science Inc, or the product is approved for marketing, or anytime at the discretion of SK Life Science Inc.
- b. Vital signs include blood pressure, heart rate (supine for 5 minutes), temperature, and respiratory rate.
- c. Height measured only at Visit 1.
- d. Brief neurological exam should be done only if symptoms require
- e. Administer the Baseline/Screening version of the C-SSRS at Screening. Administer the Since Last Visit version at all subsequent visits.
- f. 12-lead ECG will be performed once. Additional ECGs should be performed at any other time if clinically indicated.

- g. For female subjects of childbearing potential: If pregnancy is suspected at any time during the study, an interim test may be performed in addition to scheduled assessment.
- h. Laboratory assessment: Safety assessment includes blood chemistry and hematology. If the subject meets an exclusion criterion at Visit 1, an unscheduled laboratory sampling can be repeated for confirmation.
- i. Two blood samples will be collected for the determination of YKP3089 plasma levels: For patients that are taking YKP3089 in the morning and coming into the visits in the morning, the first blood draw will be collected upon subjects' arrival to the study unit; the second blood draw should be collected within 30 minutes to 2 hours after the medication is taken. Collect at visit 8 and/ or 9 depending on stability of dosing (doses must be stable for 2 weeks prior to these visits) of all concomitant AEDs including oxcarbazepine, topiramate, lamotrigine, lacosamide, clobazam, perampanel, levetiracetam, phenytoin and phenobarbital and YKP3089. YKP3089 PK draw is applicable for subjects on phenytoin and phenobarbital globally and all subjects at US sites.

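### The only neurologic shift table in SAP 13.5 uses the symptom-driven brief exam, so subjects symptom-free at Visit 2 have no stated baseline and their new on-drug findings drop out of it

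*SAP*

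**What the plan says.** SAP 13.5 describes a shift table for the physical examination: "A shift table displaying the changes from baseline to follow-up in physical examination findings will also be presented by body system". The neurologic counterpart follows in one sentence: "A similar table will be prepared for the brief neurologic exam findings". No shift table is named for the full neurologic exam. It is summarised by parameter at baseline and at follow-up, without pairing within subject. SAP 13.5 also plans by-subject listings of brief and full exams, and counts of normal and abnormal neurologic results at each post-baseline visit.

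The two exams are scheduled differently:

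- **Brief exam.** The flow chart in SAP Appendix 1 marks it at Visits 2 to 13 and every 3 months after year one. Footnote d applies to every one of these slots: "Brief neurological exam should be done only if symptoms require". SAP 8.1 and Protocol 9.1.2 both make it optional at Visit 2.
- **Full exam.** SAP 8.1 says: "A full neurologic evaluation examination will also be performed at screening and recorded on the eCRF". Protocol 9.1.1, 9.1.14 and 9.1.15 list it without condition ("Conduct full neurologic examination") at Visit 1, at Visit 14 or termination, and at Visit 15. No brief exam is listed at those three visits.

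**The concern.** A shift table counts subjects by their state before drug and their state afterwards. Its most useful safety cell is normal to abnormal. A subject enters that cell only with an examination on both sides.

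The physical examination has that structure, because every subject has a full physical at Visit 1. Carrying the layout over to the brief neurologic exam does not carry the baseline with it. If footnote d is followed, the subjects with a pre-dose brief exam are those who already had symptoms before the first dose. Subjects who were well at Visit 2 and later develop, say, nystagmus or a gait abnormality are the ones the table exists to count, and they have no brief-exam baseline.

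Protocol 9.3 says safety will be assessed by, among other things, changes from baseline in neurologic exams. For the first completed placebo-controlled trial in partial epilepsy, Protocol 4.4.3 lists the most common central nervous system adverse events as "somnolence, dizziness, fatigue, and gait disorder". Gait is an item on both neurologic forms.

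**Working it through.** The plan states no figure to reproduce, and SAP 9.1 says no formal sample size estimation was involved. The check sets the schedule, the data rules and the two forms side by side.

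**1. Which exam is available at each end of the shift** (SAP Appendix 1; Protocol 9.1)

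| Time | Brief exam | Full exam |
|---|---|---|
| Visit 1 (pre-dose) | not scheduled | scheduled for all |
| Visit 2 (pre-dose) | only if symptoms require | not scheduled |
| Visits 3–13, then every 3 months after year one | only if symptoms require | not scheduled |
| Visit 14/Termination | not scheduled | scheduled for all |
| Visit 15 | not scheduled | scheduled for all |

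The brief exam has one conditional pre-dose slot. The full exam has an unconditional slot before drug and two afterwards.

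**2. Whether another rule supplies the missing baseline**

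- SAP 10.4 takes the last non-missing pre-dose value. It does not say that an item on the full-exam form may stand in for an item on the brief-exam form.
- SAP 10.2 uses observed data. No rule codes an exam that was not required as normal.
- SAP 10.3 gives visit windows for laboratory tests, vital signs, C-SSRS, ECG and physical exam, but none for neurologic exams.

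On the plain reading, a brief-exam baseline is paired with a later brief exam, and a subject not examined at Visit 2 has no pair.

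**3. Size of the loss**

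Let q be the share of subjects with a Visit 2 brief exam. Assume q is independent of who later has a new abnormal brief exam. The documents do not give q, so the values below are assumptions. Of every 100 subjects with a new on-drug abnormality on a brief exam:

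- in the shift table = 100 × q
- lost from it = 100 × (1 − q)

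| q (assumed) | In the table | Lost |
|---|---|---|
| 5% | 5 | 95 |
| 10% | 10 | 90 |
| 25% | 25 | 75 |
| 50% | 50 | 50 |

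The share lost does not depend on how common new abnormalities are. Independence is a simplification. Subjects examined at Visit 2 because of symptoms may be more likely to be examined again, which would reduce the loss. They may also be abnormal already on the item concerned, which keeps them out of the normal-to-abnormal cell.

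**4. Whether the Visit 1 full exam could serve as baseline** (Protocol Appendices B and C)

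The full form has 25 items and the brief form 12. The shared items are level of consciousness, mental status, biceps reflexes, knee (patellar) reflexes, gait, Romberg, nystagmus, tremor, finger-nose, heel-shin and rapid alternating movements. That is 11 of 12; only general movement has no match.

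**The case against.** The strongest reply is that the SAP is silent on the baseline source, not contrary to this use. SAP 10.4 defines baseline for safety variables generally, the flow chart labels Visit 1 as the safety baseline, and 11 of the 12 brief items are recorded there. A programmer could take the baseline item by item from Visit 1, and most of the loss would disappear. The table shells are in separate documents and might say so. This stands as a possible rescue and is why the conclusion is conditional. It does not remove the point, because the SAP treats the two exams separately and nowhere allows one form to supply the baseline for the other.

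It is also fair to say that *follow-up* is undefined in SAP 13.5. The physical exam, on which the table is modelled, is not scheduled at Visit 15 either, so the word cannot simply mean that visit. If it means any post-baseline visit, the brief exam does have slots, all conditional. The missing baseline remains on either reading.

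Three stronger readings are tempting, and the documents do not support them:

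- **Symptom-free subjects can never enter the table.** This holds only if the Visit 1 full exam is ruled out as baseline, which the SAP does not do.
- **The plan cannot support the long-term safety objective.** New findings can still reach the by-visit counts, the listings and, where they qualify as adverse events, the treatment-emergent tables. None of those needs an exam baseline. Neurologic exams are also absent from the endpoint lists in Protocol 6.2.2 and SAP 7.2, although Protocol 9.3 and SAP 13 include them.
- **The by-visit percentages are inflated because only symptomatic subjects are examined.** SAP 13.5 does not state the denominator, and the brief form has a column for items not done. Inflation depends on a choice the SAP leaves open.

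Nor should the loss be stated as a number out of 1,000. That figure is the target for subjects exposed for 6 months; the safety population is everyone with at least one dose.

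**Conclusion.** The point holds in a limited form. The one paired neurologic analysis in the SAP is placed on an exam that is conditional at every slot, while an exam scheduled for all subjects before drug and at the end receives only unpaired summaries. If brief is paired with brief, the normal-to-abnormal cell loses subjects who were symptom-free at Visit 2.

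The fraction lost is 1 − q, where q is unknown. The range of 50% to 95% comes from assumed values of q from 50% down to 5%, with independence. It would shrink greatly if Visit 1 full-exam items were accepted as baseline.

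The damage is confined to one descriptive table in a study with no inferential analysis. It still merits correction: the listings, by-visit counts and adverse event tables do not give a paired change from baseline, and the data for a sound table are already scheduled.

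**What to change.** In SAP 13.5:

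1. Build the neurologic shift table from the full exam, Visit 1 to Visit 14/Termination and Visit 1 to Visit 15, with a row for missing baseline. Show the one-year Visit 14 exam separately from a later termination exam, since Protocol 9.1.16 repeats the Visit 14 assessments for subjects who stop after year one.
2. If a brief-exam shift is kept, state that the matching Visit 1 full-exam item is the baseline for the 11 shared items, and say how general movement is handled. This table would complement the first, because a transient finding between Visit 1 and Visit 14 would not show in the full-exam shift.
3. Define *follow-up* for these tables.
4. State the denominator of the by-visit neurologic percentages and print the number examined beside each one.

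The cost is SAP wording and table programming, with no new examinations or data collection. The small drawback is that the brief-exam shift in step 2 would pair two different forms, which a table footnote should say.

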13.6 Columbia Suicide Symptoms and Signs Rating Scale (CSSRS)

C-SSRS Ideation, Intensity and Behavior are collected at baseline and all post-baseline visits. Summary results of response to each question (number and percentage of subjects) will be reported by safety evaluable subgroups and overall and by study visit. The summary table will include all subjects in the safety population.

At each visit, C-SSRS responses will be mapped into Columbia-Classification Algorithm of Suicide Assessment events on as follows:

- Complete suicide = as captured in the safety database (adverse events and/or reason for discontinuation)
- Suicide attempt: “Yes” on “Actual attempt” question
- Preparatory acts towards imminent suicidal behavior: “Yes” on any of the following
 - “Aborted attempt”, or
 - “Interrupted attempt”, or
 - “Preparatory acts or behavior”.
- Suicidal ideation: “Yes” on any of the following:
 - “Wish to be dead”, or
 - “Non-specific active suicidal thoughts”, or
 - “Active suicidal ideation with any methods (not plan) without intent to act”, or
 - “Active suicidal ideation with some intent to act without specific plan”, or
 - “Active suicidal ideation with specific plan or intent”.

New onset suicidality and worsening suicidality during double-blind-phase will be assessed via a shift analysis from baseline to each post-baseline visit and to any post-baseline visit. The following shift categories will be defined:

Suicidality	Baseline Event	Any post -baseline and by visit event
New onset	No suicidal ideation and no behavior (i.e., no suicide attempt or no preparatory acts towards	Any ideation (i.e., suicide ideation) or any behavior (i.e., complete suicide, suicide attempt, or

	imminent suicidal behavior)	preparatory acts towards imminent suicidal behavior)
Worsening	Suicidal ideation	Complete suicide, or suicide attempt, or preparatory acts towards imminent suicidal behavior
	Preparatory acts towards imminent suicidal behavior	Complete suicide or suicide attempt
	Suicide Attempt	Complete suicide

The number and percentages of subjects in each of the shift categories defined above will be reported by safety evaluable subgroups and overall for all subjects included in the safety population. Missing C-SSRS responses will not be imputed.

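### The C-SSRS shift rules cannot register escalation within suicidal ideation, and no C-SSRS summary links repeat suicidal behaviour on drug to baseline

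*SAP*

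**What the plan says.** SAP 13.6 maps the C-SSRS answers at each visit to four event types: completed suicide, suicide attempt, preparatory acts (which also take in aborted and interrupted attempts) and suicidal ideation. A yes to any of five ideation items gives the same ideation category. The items run from a wish to be dead, through levels such as "Active suicidal ideation with some intent to act without specific plan", to ideation with a plan or intent.

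The shift analysis is introduced by "New onset suicidality and worsening suicidality during double-blind-phase will be assessed via a shift analysis from baseline to each post-baseline visit", and the same sentence extends it to any post-baseline visit. Two shift categories are defined:

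- New onset: neither ideation nor behaviour at baseline, then either one afterwards.
- Worsening from baseline ideation requires "Complete suicide, or suicide attempt, or preparatory acts towards imminent suicidal behavior".
- Worsening from baseline preparatory acts requires an attempt or completed suicide.
- Worsening from a baseline attempt has one qualifying outcome; the row reads "Suicide Attempt Complete suicide".

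On reporting, the section says: "The number and percentages of subjects in each of the shift categories defined above will be reported by safety evaluable subgroups and overall". The same section plans an item-level table: "Summary results of response to each question (number and percentage of subjects) will be reported by safety evaluable subgroups", by visit, in the safety population.

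On the forms used, SAP Appendix 1 (footnote e) says: "Administer the Baseline/Screening version of the C-SSRS at Screening. Administer the Since Last Visit version at all subsequent visits". SAP 10.3 sets the C-SSRS baseline at the screening visit.

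**The concern.** Protocol 6.2.2 includes change from baseline in C-SSRS among the safety endpoints. The shift analysis is the only C-SSRS summary in SAP 13.6 that ties a subject's state on drug to that subject's own baseline. If its rules cannot see some kinds of change, the reported worsening percentage is too low for those kinds, because the subjects concerned stay in the denominator without being counted.

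Two features of the rules raise this. The scale collects ideation at five levels, but the shift analysis collapses them before looking for change. And a subject who already has an attempt at baseline can enter the worsening row only through completed suicide, so a new attempt on drug does not appear in the shift result.

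Separately, the introductory sentence names a double-blind phase. Protocol 6.1 and SAP 6 both describe an open-label study, so the period named does not exist here.

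**Working it through.** The plan states no figure to reproduce, and SAP 10.1 rules out inferential analysis, so the check is an enumeration of the shift rules.

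**Step 1: categories as the SAP defines them.** Inputs, all from SAP 13.6: four baseline states (none, ideation, preparatory acts, attempt) and five post-baseline states (the same four plus completed suicide). Each subject is placed in the highest state reported. Cells: 4 × 5 = 20.

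- New onset: none to any of the 4 other states = 4.
- Worsening: 3 (from ideation) + 2 (from preparatory acts) + 1 (from attempt) = 6.
- Neither: 20 − 4 − 6 = 10.

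The 10 cells in neither category are none-to-none (1), moves to a lower state (6) and same-category cells with an event on both sides (3): ideation to ideation, preparatory to preparatory, attempt to attempt. One of the six downward cells, attempt to preparatory acts, also contains suicidal behaviour on drug.

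**Step 2: ideation items kept separate.** The five items are taken as ordered in the SAP list, lowest first, followed by preparatory acts, attempt and completed suicide.

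| Baseline state | Higher states possible | Counted as worsening | Not counted |
|---|---|---|---|
| Ideation item 1 | 7 | 3 | 4 |
| Ideation item 2 | 6 | 3 | 3 |
| Ideation item 3 | 5 | 3 | 2 |
| Ideation item 4 | 4 | 3 | 1 |
| Ideation item 5 | 3 | 3 | 0 |
| Preparatory acts | 2 | 2 | 0 |
| Attempt | 1 | 1 | 0 |
| Total | 28 | 18 | 10 |

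The 10 uncounted upward moves are the pairs within ideation: 5 × 4 / 2 = 10. Every upward move into or between behaviour categories is counted. The missed worsening therefore lies entirely within ideation.

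**Step 3: where else these subjects would show.**

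- Item-level table (SAP 13.6): each ideation level and each behaviour item is counted by visit, whatever the baseline. It is not cross-classified by baseline, and no any-time count is planned for it. By contrast, SAP 13.2 plans any-time post-baseline counts for liver tests, and SAP 13.4 counts subjects with at least one qualifying vital sign.
- Adverse event outputs (SAP 13.1): an attempt reported as an adverse event with onset after first dose would be in the treatment-emergent tables and, if serious, in the serious event table and listing. These outputs do not use the C-SSRS baseline. A rise in ideation recorded only on the scale need not reach them.

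**The case against.** The best defence is that a shift table records movement between categories. Attempt to attempt and preparatory to preparatory are not movement, so leaving them out of worsening is a defensible definition. This stands: such repeats are recurrence on treatment and need not be deterioration. What remains is that no C-SSRS summary relates the recurrence to baseline.

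The second defence is that nothing is hidden. Attempts on drug are in the item-level table and, when reported as events, in the adverse event outputs. This stands for visibility of the events themselves. It does not supply change within a subject, which is what the endpoint asks for, and it does little for escalating ideation.

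The third is that the analysis is descriptive, without a control arm, and that the reference to a double-blind phase is a slip: the same sentence already fixes the comparison as baseline to each and any post-baseline visit. That is fair, and the slip is unlikely to alter the analysis.

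A reader might also infer three stronger things that the documents do not support:

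- That these subjects are labelled as unchanged. No such category exists; they are simply uncounted in the shift table.
- That every repeat is serious deterioration. The table cannot show that.
- That a definite share of subjects with a past attempt can never register a new one. The documents give no baseline rate of suicidality. The recall period of the screening form is not in the supplied text, and the exclusion criteria as supplied do not settle whether such subjects could enrol.

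**Conclusion.** The point holds for escalation within ideation: 10 of 28 possible upward moves from a non-zero baseline fall in neither shift category. This is a count of possible transitions, not of subjects; the number of subjects affected cannot be computed and could be small. For repeat behaviour the finding is narrower: it is uncounted in the shift table and not tied to baseline elsewhere in the C-SSRS summaries, but it is not missed worsening.

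Two assumptions matter. The SAP's list order of the ideation items is read as increasing severity. Each subject is placed in the highest baseline category, which SAP 13.6 does not state; if rows were applied without that hierarchy, a subject with both ideation and an attempt at baseline could be counted through the ideation row after a repeat attempt. The within-ideation gap does not depend on the second assumption.

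This is a worthwhile, inexpensive improvement to a descriptive safety analysis of a serious outcome.

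**What to change.** 1. Add to the worsening category a higher maximum ideation item (1 to 5) after baseline than at baseline, reported by visit and at any post-baseline visit.
2. Add an any-time count of subjects with suicidal behaviour (completed suicide, attempt or preparatory acts) after first dose, regardless of baseline and split by baseline category. Label repeats as recurrence. Say that the highest baseline category is used and which period the screening form covers.
3. Replace the reference to the double-blind phase with the open-label treatment period. This is a wording correction.

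The cost is one more table block per summary group, programmed from C-SSRS and safety data already collected. Reported counts of worsening may rise. If merging the ideation items is deliberate, the SAP should say so and give the reason.
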